4.2.4.2. Analysis Methods

To compare incidences across treatment groups (for the need for ICU stay, oxygen support, supplemental feeding or supplemental hydration, for the all-cause mortality, for the subjects with undetectable viral load per time point and for the presence of complications), logistic regressions will be used, with treatment as fixed effects and strata as part of the stratifying variables (ie. stratified logistic model). Other covariates and or baseline indicators may be included in the model when of predictive value, such as baseline \log_{10} viral load, smoker (yes/no), the presence/absence of co-morbid diseases, presence/absence of co-morbid diseases associated with risk for lower respiratory tract disease, presence/absence of other conditions/therapy of potential interest, days since symptom initiation, RSV subtype, use of corticosteroids, supplemental oxygen at baseline and age as continuous variable. Stepwise selection will be used to identify the prognostic factors for each of the different models for the different incidence parameters. A significance value of 0.05 is required for a variable to enter the model and a significance value of 0.10 is required to stay in the model. The odds ratios including 95% confidence interval of active groups versus placebo will be derived from the final model using appropriate contrasts. Exact logistic regression models will be used in case the incidence of the events is low (< 10 events).

Time-to-events variables will be analyzed in an exploratory sense using Kaplan-Meier analysis, A summary table including number of subjects included in the analysis, number of subjects censored, 25th and 75th percentiles and median time to event, with 95% confidence intervals based on log-log transformation method, will be presented. The data will be presented graphically using the Kaplan-Meier estimate of the survival function.

If specified, time-to-events variables will also be compared between each active treatment group and placebo using an accelerated failure time (AFT) model. The distribution to be used will be determined based on the goodness of fit using Akaike's information criterion and will be selected from the following parametric families: lognormal, log-logistic, or Weibull. The AFT model will include the fixed, categorical effects for treatment (with placebo as the reference) and strata, as well as the continuous covariates of baseline \log_{10} viral load. Other covariates may be included when of predictive value, such as smoker (yes/no), presence/absence of co-morbid diseases, presence/absence of co-morbid diseases associated with risk for lower respiratory tract disease, presence/absence of other conditions/therapy of potential interest, days since symptom initiation, RSV subtype, use of corticosteroids, supplemental oxygen at baseline and age as continuous variable. As in the logistic regression, a significance level of 0.05 will be used for a variable to enter the model and a significance value of 0.10 to stay in the model. A summary of information from the final model will include parameter estimates and associated standard errors, estimated accelerated failure time ratios versus placebo and associated 95% confidence intervals, and p-values.

Length of Hospital Stay/Length of Hospital Need

The Length of Hospital Stay/Need (both since treatment initiation and since hospital admission) will be summarized and listed. The Length of Hospital Stay/Need will be analyzed in an exploratory manner using Kaplan-Meier analysis.

Length of Hospital Stay/Need will also be compared between each active treatment group and placebo using an accelerated failure time (AFT) model as described above.

Need and Duration of ICU Stay

The need for ICU stay will be analyzed on the subgroup of subjects who were not in the ICU before the first dose of study medication. The duration in the ICU will be analyzed all subjects and on both the subgroup who were and who were not in the ICU before the first dose of study medication.

The number and percentage of subject with need of ICU stay, and the duration of ICU stay in hours, will be summarized descriptively.

To compare incidence of the need for ICU stay across treatment groups, (exact) logistic regression as described before will be used.

Need and Duration of Oxygen Support, Supplemental Feeding, Supplemental Hydration

The need and duration of supplemental oxygen will be analyzed by splitting the ITT-i population into two partitions:

- 1) Those patients who require supplemental oxygen before treatment initialization
- 2) Those patients who did not require supplemental oxygen before treatment initialization

Both partitions will be analyzed separately, answering two different questions:

- 1) For those patients who require supplemental oxygen before treatment initiation: Is there a treatment difference in the time to no longer requiring supplemental oxygen? This analysis will be performed primarily with a Kaplan-Meier analysis and a stratified Gehan test.
- 2) For those patients who did not require supplemental oxygen before treatment initialization: Is there a treatment difference in preventing the use of supplemental oxygen? This partition will be analyzed using a stratified (exact) logistic regression model as specified above.

While we cannot integrate these results they are conceptually linked. We will combine the p-values for both independent tests for the comparison of each active group versus placebo using the method of Liptak^[3].

In addition to the analysis described above, the time to no longer requiring supplemental O₂ will be analyzed on the total group of subjects where subjects who do not require supplemental oxygen during the study are considered to have their event at time 0. As before, this will be analyzed in an exploratory sense using Kaplan-Meier analysis and with a stratified Gehan test to test for treatment differences.

This analysis will be repeated by method of administration (invasive, non-invasive).

The analysis for the need and duration of supplemental feeding and supplemental hydration will be done in similar fashion as for supplemental oxygen use described above.

Time to SpO₂ ≥ 93% (hours) on room air

Time to SpO₂ ≥ 93% (hours) on room air will be summarized and listed for subjects who were not on supplemental oxygen prior to current hospitalization.

Among subjects who were not on supplemental oxygen prior to current hospitalization, the time to SpO₂ ≥ 93% (hours) on room air, will be summarized and analyzed in an exploratory sense using Kaplan-Meier analysis.

The time from first dose to SpO₂ ≥ 93% (hours) on room air will also be analyzed using AFT methodology.

Time to return to pre-RSV disease level (hours) for RR, SpO₂; body temperature

The time to return to pre-RSV disease level (hours) for RR, SpO₂ and body temperature will be analyzed using the same approach as for the Time to SpO₂ ≥ 93% (hours) on room air.

Time to return to pre-RSV functional status (KATZ ADL score) (days)

Time to return to pre-RSV functional status (KATZ ADL score) (days) will be analyzed using the same approach as for the Time to SpO₂ ≥ 93% (hours) on room air.

Time to clinical stability (hours)

The time to clinical stability (hours) will be analyzed using the same approach as for the Time to SpO₂ ≥ 93% (hours) on room air.

Ordinal scale

The number and percentage of subjects will be summarized for the ordinal scale by treatment group at the end of the treatment period (Day 5/6).

The analysis will be performed using a proportional odds model, modeling the common odds ratio of the improvement on the ordinal scale of each active treatment versus control. Age category (≥50 to <65 years and ≥65 years) and region (Japan, non-Japan) will be added to the model as fixed factors. For each of the 5 possible cut-points the odds ratio will also be presented (comparing active versus placebo) to verify the common odds assumption.

For the ordinal scale also descriptive statistics will be computed for each post-baseline day (days 3 to 14 and day of last dose). Here missing data will be imputed using the LOCF approach.

All-cause mortality

The number and percentage of subjects who died will be summarized and compared between treatment groups using the logistic regression approach described before.

Note that this analysis will only be performed if any deaths did occur.

Viral load over time

Descriptive statistics and mean (SE) plots will be shown for the log₁₀ values of RSV RNA viral load and the changes from baseline calculated in log₁₀(copies/ml) by treatment group.

Peak viral load/Rate of decline:

The log peak viral load and rate of decline of RSV RNA viral load will be compared for active groups versus placebo groups using a general linear model with treatment and strata included as fixed effects. Other covariates and or baseline indicators may be included in the model when of predictive value, such as baseline log₁₀ viral load, smoker (yes/no), presence/absence of co-morbid diseases, presence/absence of co-morbid diseases associated with risk for lower respiratory tract disease, presence/absence of other conditions/therapy of potential interest, days since symptom initiation, RSV subtype, use of corticosteroids, supplemental oxygen at baseline and age as continuous variable. Stepwise selection will be used to identify the prognostic factors. A significance value of 0.05 is required for a variable to enter the model and a significance value of 0.10 is required to stay in the model.

Residuals of the final model will be plotted in a normal probability plot; in case the model does not fit the log peak value data well, the log transformation (ie. the log of log peak viral load) will be considered as dependent variable. The data from the model will be reported as (adjusted)

differences in least squares (LS) means (in the case of untransformed data) or (adjusted) geometric mean ratios (in case of log-transformed data) of active dose groups versus placebo, including 95% confidence intervals using appropriate contrasts.

Time to Peak viral load:

Time to Peak viral load will be analyzed using the same approach as for the Time to SpO₂ ≥ 93% (hours) on room air.

Time to RSV RNA being undetectable:

Time to RSV RNA being undetectable will be analyzed using the same approach as for the Time to SpO₂ ≥ 93% (hours) on room air.

In addition, the differences in time to RSV RNA being undetectable of active dosing regimens versus placebo treatment will be estimated using the accelerated failure time model based on interval censored data. Treatment and stratum will be added as fixed categorical effects, while log baseline viral titer will be added as a continuous fixed covariate.

Treatment effect versus placebo will be reported as an acceleration factor including 95% confidence intervals for each active treatment group. Estimated survival curves will be created based on the mean baseline titer value and weighted average for each stratum.

Proportion of subjects with undetectable viral load at each time point:

The proportion of subjects with a negative viral shedding titer will be tabulated at each timepoint (with corresponding 95% CI). In addition, the same logistic regression approach as described before will be used to obtain the odds ratios (95% CI) for each comparison versus placebo.

RSV RNA viral load AUC until Day 10 and until Day 14

The same model used for the primary analysis will be used to test for a dose response relationship on the AUC until Day 10 and until Day 14. No corrections for multiplicity will be made, thus the significance level of α (α^*) will be kept at 0.05.

The differences in the AUCs for active versus placebo will be derived using appropriate contrasts deriving least square mean differences, including the 95% 2-sided confidence intervals.

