
[Time-to-event] (3 separate parameters: overall, invasive, non-invasive)
 
Time to end of supplementation feeding, hydration (hours) [Time-to-event] (2 separate parameters)
	
study drug)/3600, rounded to one decimal
 
The event is defined as the last end date and time of the measured parameter (supplemental oxygen, invasive oxygen, non-invasive oxygen, feeding or hydration). If this date is missing, the end date is considered to be after study completion or withdrawal.
 
Subjects who complete or withdraw from the study prior to the last end date and time of the measured parameter will be censored at the date of completion or withdrawal. If the time is not available they will be censored at 12:00. In case of death prior to the last end date and time of the measured parameter, the time of death will be taken as censoring time (or 12:00 if not available).
 
If no oxygen supplementation, supplemental feeding or hydration was necessary post baseline, the value will be set to 0.

Time point of SpO2 \geq 93% on room air
	
The first time point with SpO2 \geq 93%, where no supplemental oxygen supplementation is given at or after this time point and where no value $<$ 93% are measured after this time point.

Time to SpO2 \geq 93% (hours) on room air [Time-to-event]
	
minimum[date and time of time point with SpO2 \geq 93% on room air, date and time of last SpO2 measurement] - date and time of first dose of study drug)/3600[†], rounded to one decimal
 
Subjects with SpO2$<$93% on room air or who are still on oxygen supplementation at the last SpO2 assessment will be censored at the date and time of the last SpO2 assessment.
 
This parameter will only be calculated for subjects who were not on supplemental oxygen prior to current hospitalization

Time point of return to pre-RSV disease level (hours) for HR, RR, SpO2 (3 separate parameters)
	
The first time point where it is indicated by the investigator that the observed value is normal for the subject, and for none of the time points after this point in time the values are indicated to be abnormal for the subject (separate for HR, RR or SpO2).

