
Time to return to pre-RSV disease level (hours) for HR, RR, SpO2 [Time-to-event]
	
(minimum[date and time of time point of return to pre-RSV disease level, date and time of last measurement] - date and time of first dose of study drug)/3600, rounded to one decimal
 
If none of the values are indicated to be abnormal for the subject, this value will be set at time 0.
 
Subjects with an abnormal value at the last assessment will be censored. Subjects for which this last assessment is the baseline

	assessment will be censored at time 0.
Time to return to pre-RSV disease feeding status (hours) [Time-to-event]	
(Date and time of event or censoring - date and time of first dose of study drug)/3600, rounded to one decimal
 
All subjects are assumed to have no supplemental feeding pre-RSV.
 
The event is defined as the last available end date and time supplemental feeding was provided. If this date is missing, the end date is considered to be after study completion or withdrawal
 
Subjects who complete or withdraw from the study prior to the event will be censored at the date of completion or withdrawal. If the time is not available they will be censored at 12:00. In case of death prior to an event the time of death will be taken as censoring time (or 12:00 if not available).
 
If no supplemental feeding was necessary post baseline, the value will be set to 0.

Time to Clinical Stability [Time-to-event]	
maximum[time to return to pre-RSV disease level for SpO₂, RR and HR, feeding]
 
Subject will be censored if the subject is censored for at least 1 of the 4 time to parameters at the minimum of the available data. If no data are available the time will be censored at 0 hours.

Time point of return to normal temperature (hours) [Time-to-event]	
All subjects are assumed to have a normal temperature level pre-RSV disease
 
Time point of return to pre-RSV disease level temperature is defined as the first time point with a normal temperature and no time points after that time point with an abnormal value.
 
The normal limits to be used are:
 
 - Axillary: 36.1 – 38.0 - Forhead: 36.1 – 38.0

	
 - Oral: 36.1 – 38.0 - Rectal: ≤ 37.2 - Tympanic: ≤ 37.8 
If there were no abnormal values post baseline, the value will be set at 0 hours.

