Time to normal temperature (hours) [Time-to event]	
Minimum[date and time of Time of return to pre-RSV disease level temperature, date and time of last measurement] - date and time of first dose of study drug)/3600[†], rounded to one decimal
 
If none of the values are abnormal for the subject, this value will be set at time 0.
 
Subjects with an abnormal value at the last assessment will be censored. Subjects for which this last assessment is the baseline assessment will be censored at time 0.

Time point of return to pre-RSV functional status (KATZ ADL score)	
The first time point where the KATZ ADL score is equal or higher than the pre-RSV disease KATZ ADL score and no lower scores are measured after this time point.
 
Functional status is the total points on the KATZ Index of Independence in Activities of Daily Living (KATZ ADL score)

Time to return to pre-RSV functional status (KATZ ADL score) (days) [Time-to-event]	
minimum[date and time of time of return to pre-RSV functional status, date and time of last measurement] - date and time of first dose of study drug)/3600, rounded to one decimal
 
If the KATZ ADL score is never lower than the pre-RSV score, this value will be set at time 0.
 
Subjects with a functional status lower than the pre-RSV disease functional status at the last KATZ ADL assessment will be censored. Subjects for which this last assessment is the baseline assessment will be censored at time 0.

Ordinal scale score	
The value as collected in the eCRF on the day of last dose (Day 5/6 depending on timing of LD) will be used as score on the day of last dose. Only in case of a missing score, the score will be calculated based on the available information in the eCRF.
 
The 6 categories to be considered are:

	
 • Death • Admitted to ICU • Non-ICU hospitalization requiring supplemental oxygen • Non-ICU hospitalization not requiring supplemental oxygen • Not hospitalized, unable to resume normal activities • Not hospitalized, resumption of normal activities 
Subjects will receive a score ranging from 1 (=subject died on or before of their day of last dosing) to 6 (=subject was not-hospitalized, resumption of normal activity) depending on his status on day of last dosing
 
For days 3 to 14, the ordinal scale will be calculated on each day, using the algorithm described above.

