All-cause mortality	Subjects who died during the study will receive code 1, subjects who survive will receive code 0
Peak viral load	Highest value of viral load at or after the baseline measurement.
Time to peak viral load (hours) [Time-to-event]	
Defined as the relative time in hours from the first dose of study drug until the first time point when the viral load reaches the peak viral load.
 
Subjects for which the peak was reached at the baseline measurement will have time 0.
 
Subjects for whom the peak is reached at the last observed time point will be censored. Subjects for which this last assessment is the baseline assessment will be censored at time 0.

Rate of decline of viral load over the first 24 hours	
calculated as a log decline/24 hours defined as: $(24\text{-hour log viral load after first dose of study drug} - \text{log viral load at baseline}) / (\text{date/time of 24-hour viral load sample} - \text{date/time of baseline viral load})$
 
Note, the 24-hour viral load may not have been measured at exactly 24 hours following first dose, but the actual date/time associated with the 24-hour viral load will be used in computing the viral load slope. In case the 24 hour measurement is not

	available the slope will be calculated using the Day 3 assessment (48 hours), using the same definition. If there is no measurement in that time frame, the slope will not be calculated.
Time to non-detectability (hours) [Time-to-event]	
Defined as the relative time in hours from the first dose of study drug until the first post baseline time point when the viral load reaches non-detectability and no detectable values are measured after this time point.
 
For each subject in the ITT-i it will be assumed that the subject is positive at baseline (even if the value is negative).
 
Subjects whose viral load does not reach non-detectability will be censored at the relative time in hours from the first dose of study drug until this last RSV assessment. Subjects for which this last assessment is the baseline assessment will be censored at time 0.

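### Several secondary endpoints are given event times of exactly zero in SAP Table 1 and are then compared by AFT models on log time, which cannot use a zero event

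*SAP*

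**What the plan says.** SAP 4.2.4.2 sets out an AFT comparison of each active arm with placebo. The distribution is picked by Akaike's criterion and "will be selected from the following parametric families: lognormal, log-logistic, or Weibull". For time to SpO2 of at least 93% on room air, the section prescribes Kaplan-Meier summaries plus this AFT model. The paragraphs on respiratory rate (RR), SpO2, temperature, Katz ADL, clinical stability and time to peak viral load refer back to that approach.

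Table 1 in SAP 4.2.4.1 creates the zeros:

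- Return to pre-RSV heart rate, RR or SpO2: "If none of the values are indicated to be abnormal for the subject, this value will be set at time 0".
- Temperature, time-point row: "If there were no abnormal values post baseline, the value will be set at 0 hours".
- Temperature, time-to-event row: "If none of the values are abnormal for the subject, this value will be set at time 0".
- Katz ADL: "If the KATZ ADL score is never lower than the pre-RSV score, this value will be set at time 0".
- Time to peak viral load: "Subjects for which the peak was reached at the baseline measurement will have time 0".

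Censoring in these rows applies only to subjects still abnormal (or below their pre-RSV Katz score) at the last assessment, or peaking at the last time point. The zeros are therefore uncensored events. Neither document gives an offset, an exclusion, an interval-censoring rule or a two-part model for them.

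For supplemental oxygen, the same section also places some events at time 0. There it uses Kaplan-Meier and a stratified Gehan test, analyses subjects separately by oxygen need before treatment, and combines the two p-values by Liptak's method.

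**The concern.** The data rule and the model do not fit together. For RR, SpO2, temperature, Katz ADL and time to peak, the AFT ratio with its interval and p-value is the only between-arm comparison the SAP states. Kaplan-Meier is described as exploratory, and no Gehan test is named for these endpoints. If zeros cannot enter the model, that comparison depends on a choice nobody has written down and which could be made after the data are seen.

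Zeros are to be expected. Protocol 4.1 lists fever and shortness of breath only as examples of qualifying symptoms, and no criterion requires an abnormal temperature, RR, SpO2 or Katz score at entry.

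Zero status also depends partly on readings after randomisation: a subject must stay normal, or have no later viral load above baseline. Leaving such subjects out removes any treatment effect on staying normal and no longer compares all randomised subjects in ITT-i.

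**Working it through.** **Inputs.** The zero rules come from SAP Table 1, the model families and routing from SAP 4.2.4.2, and the 30 subjects per arm from SAP 1.2. The plan states no figure on this point, so there is none to reproduce. Zero shares, effect size and spread below are assumptions.

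**Step 1: can the model take a zero?** Log-density of an exact event at time t:

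- Lognormal: -log t - log σ - ½ log 2π - (log t - μ)²/(2σ²). As t goes to 0 the squared term dominates and the value goes to minus infinity.
- Weibull and log-logistic with shape k and scale λ: near zero both behave as log k - k log λ + (k - 1) log t. This goes to minus infinity for k > 1 and plus infinity for k < 1. It is finite only at k exactly 1, where it equals -log λ (at λ = 48 h, -3.87).

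So one zero event makes the likelihood degenerate. A subject censored at 0 contributes log S(0) = 0, so rules such as "Subjects for which this last assessment is the baseline assessment will be censored at time 0" cause no difficulty.

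**Step 2: how many subjects could be lost?** Dropping a share p of 90 leaves 90 × (1 - p): 81 at 10%, 72 at 20%, 54 at 40%.

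**Step 3: what does each unstated choice do?** Simulation: 4,000 trials per setting, 30 versus 30, lognormal times, log SD 1.0, true ratio 0.60, no covariates or censoring. The lognormal AFT is then a t-test on log times.

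Setting A: zeros are subjects normal throughout, equally frequent by arm; placebo median of positive times 48 h.

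| Zeros in each arm | 10% | 20% | 30% | 40% |
|---|---|---|---|---|
| Dropped: ratio | 0.60 | 0.60 | 0.60 | 0.60 |
| Dropped: power | 44.8% | 40.6% | 36.4% | 31.2% |
| 0.1 h entered: ratio | 0.63 | 0.67 | 0.70 | 0.73 |
| 0.1 h entered: power | 15.5% | 10.2% | 8.0% | 7.0% |
| 1 h entered: ratio | 0.63 | 0.67 | 0.70 | 0.74 |
| 1 h entered: power | 23.4% | 15.5% | 11.7% | 9.3% |
| Gehan, all subjects: power | 32.6% | 22.4% | 15.9% | 10.7% |

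The substituted ratios can be checked by hand. With equal zero shares p, the mean log difference is (1 - p) × log 0.60, so the ratio is 0.60^(1 - p): 0.63, 0.67, 0.70, 0.74. Power falls because log 48 - log 0.1 = 3.87 + 2.30 = 6.17, so the substituted values lie about six log SDs below the placebo median.

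Setting B: 20% or 40% are normal at baseline; 40% of these deteriorate on placebo and 20% on active. Dropping zeros gives ratios 0.60 and 0.61 with power 43.5% and 34.6%. A split on baseline status combined by Liptak has 41.9% and 43.6%. The cost of ignoring an effect on staying normal appears at the larger share.

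Setting C, a worst case for temperature: every zero is a recovery before a 12 h reading, giving zeros of 10-40% on placebo and 22-60% on active. Dropping gives ratios 0.72-0.82 with power 28.4-11.0%. Entering 0.1 h gives 0.36-0.29; entering 1 h gives 0.45-0.48.

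With a true ratio of 1.0, rejection was 4.1-5.5% for every method in these settings.

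**Step 4: the model choice moves too.** In a smaller run (60 replicates, true ratio 0.80, log SD 0.8, 20% zeros per arm), Akaike's criterion chose lognormal in 37 replicates when zeros were dropped, and Weibull in all 60 for every substitute value tried.

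**Step 5: adjoining rules.** Take a subject febrile at baseline and normal at every later reading. The temperature time-point row looks only after baseline and gives 0. Read alone, the time-to-event row asks that no value be abnormal, so it would give the time of the first normal reading. For SpO2 of at least 93%, the qualifying time point is one "where no supplemental oxygen supplementation is given at or after this time point" and with no later value below 93%. Unlike the other rows, it has no rule for a time at or below zero. Clinical stability is the maximum of four times, so it is 0 only when all four are 0.

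**The case against.** The strongest reply is that leaving zeros out does little harm. In setting A it is unbiased and has the highest power of the methods compared; in setting B the ratio is 0.60-0.61. No passage proposes entering 0.1 h or 1 h, so the worst ratios come from hypothetical choices. This stands as to size. It does not supply the missing rule, and it does not recover an effect on staying normal.

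Some stronger readings are tempting, but the documents do not support them.

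- *Dropping zeros biases these endpoints in general.* Serious bias from dropping appeared only in setting C. That needs the temperature time-point row and assumes that every zero is an early recovery. The row also gives 0 to subjects afebrile throughout, so real zeros would be a mixture.
- *The two temperature rows flatly contradict each other.* They can be read as a chain, because the second row takes the first row's time point as input, and that is already 0. The wording is ambiguous rather than irreconcilable.
- *The SAP is silent on pre-dose SpO2 readings.* SAP 2.1 says scheduled assessments after the first administration are used, and SAP 4.2.4.2 describes this endpoint as timed from first dose. These bear on the question without settling it in Table 1.
- *The main result or the error rate is at risk.* The alpha-controlled test in SAP 4.2.1.1 concerns the primary AUC only, and the simulations show no inflation.

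The magnitudes rest on assumed inputs, and time to peak was not simulated separately.

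**Conclusion.** The point holds as an incompatibility between a stated data rule and a stated model, for return to pre-RSV RR, SpO2 and temperature, for Katz ADL and for time to peak viral load. Time to clinical stability is affected only when all four components are zero, which may be uncommon.

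Its size in this trial cannot be given, since zero shares are not in the documents. On the assumptions shown, dropping zeros is nearly unbiased when they mark subjects normal throughout and are balanced by arm. A small substitute value can change both the ratio and the power substantially. The primary AUC, Kaplan-Meier summaries, length of stay and subjects censored at 0 are unaffected. It should be corrected before unblinding, but it does not threaten the trial's main conclusion.

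**What to change.** 1. RR, SpO2, temperature and Katz ADL: adopt the split already used for oxygen. Among subjects abnormal at baseline, analyse time to return by AFT; with rule 3 in place these times are positive. Among subjects normal at baseline, compare the incidence of becoming abnormal by the stratified logistic model. Report both parts, and combine by Liptak if one p-value is wanted. Each part then compares randomised groups.
2. Time to peak viral load: replace the AFT with the stratified Gehan test on all subjects, plus a logistic comparison of peak at baseline versus later.
3. Use one temperature rule in both rows, so that a subject febrile at baseline and normal afterwards gets the time of the first normal reading. State that only post-dose readings count for SpO2 of at least 93%, consistent with SAP 2.1.
4. Time to clinical stability: reconcile the AFT in SAP 4.2.4.2 with the Cox model in protocol 11.3. This is a separate mismatch, but Cox accepts ties at 0.

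The cost is SAP wording and modest programming, with methods already in the documents. There are statistical costs as well. Liptak loses power when only one part carries the effect, and the Gehan test gives no time ratio. Cox has less power than AFT on positive times if times are lognormal. In 1,500 simulated trials under setting A's assumptions, it had 40% versus 48% at 5% zeros and 29% versus 41% at 20%.
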